10.2. Clinical Laboratory Evaluations

Clinical laboratory tests (including serum chemistry, hematology, urinalysis, lipid panel, hormones, and hepatitis serology) will be collected per the timing presented according to the protocol. All summaries will be based on the International System of Units (SI) and the central lab results. Laboratory values that are below the limit of quantitation (LLOQ) or above the upper limit of quantitation (ULQ) will be assigned the numerical part of the results.

10.2.1. Hematology

Descriptive statistics of observed and change from baseline values will be presented by treatment group and total at the scheduled visits for white blood cell count including differential, red blood cell count, hemoglobin, hematocrit, and platelet count. A shift table representing the change from baseline to the worst post-baseline values in normal, low, or high will also be provided by treatment group and total. A subject could be counted in both low and high categories if the subject experiences both low and high in the post-baseline visits.

A listing will be provided for all hematology tests by study phase and local lab data will be flagged in the listing. In addition, a listing of hematology tests will be provided for subjects with any clinically significant abnormality.

10.2.2. Serum Chemistry

Descriptive statistics of observed and change from baseline values will be presented by treatment group and total at the scheduled visits for alanine aminotransferase, albumin (total), alkaline phosphatase, aspartate aminotransferase, bilirubin (total), blood urea nitrogen, calcium, chloride, creatinine level, creatine phosphokinase, c-reactive protein, gamma-glutamyl transferase, glucose, HbA1C, phosphorus, potassium, protein (total), sodium and urate. A shift table representing the change from baseline the worst post-baseline values in normal, low, or high will also be provided by treatment group and total. A subject could be counted in both low and high categories if the subject experiences both low and high in the post-baseline visits.

A listing will be provided for all chemistry tests and local lab data will be flagged in the listing. In addition, a listing of chemistry tests will be provided for subjects with any clinically significant abnormality.

10.2.3. Hormone

Descriptive statistics of observed and change from baseline values will be presented by treatment group and total at the scheduled visits for parathyroid hormone, 25-Hydroxy vitamin D, and 1, 25-Dihydroxy vitamin D.

A listing will be provided for all hormone tests by subject and visit.

10.2.4. Lipid Panel

Descriptive statistics of observed and change from baseline values will be presented by treatment group and total at the scheduled visits for cholesterol (total), high density lipoprotein, low density lipoprotein and triglyceride.

A listing will be provided for all lipid panel tests by subject and visit.

10.2.5. Urinalysis, Hepatitis serology, Tuberculosis Testing and Pregnancy Testing

Listings will be provided for urinalysis, hepatitis serology tests, tuberculosis testing, and pregnancy testing by subject and visit.

10.3. Vital Sign Measurements

Vital sign measurements include pulse rate (beats per minute), systolic blood pressure (mmHg), diastolic blood pressure (mmHg), respiratory rate (breaths per minute), weight (kg), and BMI (kg/m^2) as collected on the eCRF. Descriptive statistics will be provided for observed and change from baseline values by treatment group and total at the scheduled visits.

All vital signs will be presented in a listing by study phase.

10.4. Physical Examination

The number and percentage of subjects with different response (Normal, Abnormal Not Clinically Significant, and Abnormal Clinically Significant) will be summarized for each physical assessment by treatment group and total at scheduled visits.

All physical examination results will be presented in a listing by study phase.

10.5. Electrocardiogram

The 12-lead electrocardiogram (ECG) assessments include heart rate (beats per minute), PR interval (milliseconds), RR interval (milliseconds), QRS duration (milliseconds), QT interval (milliseconds), and QTcB (milliseconds). Descriptive statistics will be provided for observed and change from baseline values by treatment group and total at the scheduled visits.

The number and percentage of subjects with each ECG overall interpretation (Normal, Abnormal Not Clinically Significant, and Abnormal Clinically Significant) and the number and percentage of subjects with normal sinus rhythm (Yes, No) will be summarized by treatment group and total at scheduled visits.

All ECG assessments will be presented in a by-subject listing by study phase.

11. Biomarker Analysis

11.1. Biomarkers

Descriptive summary will be provided to describe the selected biomarker endpoints using the safety population by treatment group, if data is available. The selected biomarker endpoints may include angiotensin-converting enzyme, sIL-2R and vitamin D 1,25. The final determination as to the selection of biomarkers will be made based on the evolution of the science and emerging guidance closer to the completion of the study. Descriptive

statistics will be provided for observed and change from baseline values for each selected biomarker at scheduled visits.

All biomarker data will be presented in a listing by subject and visit.

11.2. Genetic Profile

Genetic sample obtained for subjects who has signed the genetic inform consent form at study entry may be explored and presented in tables. Descriptive statistics will be provided if data is available.

All genetic data will be presented in a listing.

12. Interim Analysis

No formal interim analysis is planned.

13. Changes in the Planned Analysis

The summary of changes presented below reflects the changes in the planned analysis described in protocol:

- The protocol planned endpoint analysis for “Change from baseline in WPAI over time” will not be performed given very few subjects have taken WPAI questionnaire. WPAI data will be only presented in listings.
- The protocol planned endpoint analysis for “Time to response (TTR) as evaluated at earlier time points (Weeks 4 to 20) as determined by the investigator based on clinical judgment” will not be performed.
- The protocol planned analysis for biomarker and genetic endpoints may not be performed depending on the availability of the data.

14. References

Judson MA. Advances in the diagnosis and treatment of sarcoidosis. *F1000Prime Reports* 2014; 6: 89.

Mallinckrodt ARD, Inc. A Phase 4 Multicenter, Randomized, Double Blind, Placebo Controlled Pilot Study to Assess the Efficacy and Safety of H.P. Acthar® Gel in Subjects with Pulmonary Sarcoidosis. Original, 06 October 2017.

15.Appendices

15.1. Date Imputation Guideline

15.1.1. Adverse Events

Missing start dates for AE data will be handled as follows:

- Missing day only:
 - If the month and year are the same as the first dose month and year, then it will be imputed as the date of the first dose.
 - If either the year is the same as the first dose year, but the month is prior to the first dose month or the year is prior to the first dose year, then it will be imputed as the last day of the collected month.
 - If either the year is the same as the first dose year, but the month is after the first dose month or the year is after the first dose year, then it will be imputed as the first day of the collected month.
- Missing day and month:
 - If the year is the same as the first dose year, then it will be imputed as the date of the first dose.
 - If the year is prior to the first dose year, then it will be imputed as December 31st of the collected year.
 - If the year is after the first dose year, then it will be imputed as January 1st of the collected year.
- Missing day, month and year:
 - It will be imputed as the date of the first dose.

No imputation will be applied to the missing or partial stop dates for AEs. If the AE end date is complete and the partial AE start date imputed by the rules above is after the AE end date, then the start date will be imputed by the AE end date.

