4.3. Reporting Conventions

The following reporting conventions apply generally to tables, listings, and figures:

- All by-visit summaries and analyses will be provided separately for the double-blind treatment phase and the open-label extension phase, unless otherwise specified. Only subjects who continued to the open-label extension phase will be included in the summaries of open-label extension phase based on the open-label safety populations.

- For subjects who continued into the open-label extension phase, the first dose of IMP at the open-label extension phase will be used as the cutoff date. Since the first dose administration date at the open-label extension phase is not collected electronically, and the dosing schedule is twice/week, either the first IMP kits and equipment dispense date or the next date after completion date of double-blind phase, whichever is the later date, has been used as the best estimate of the first dose of IMP in the open label extension phase. The assessments collected before the cutoff date will be summarized in the double-blind treatment phase and the assessments collected on or after the cutoff date will be summarized in the open-label extension phase, unless specified otherwise. Subjects who did not continue into the open-label extension phase will be summarized in the double-blind treatment phase only.
- Summaries for the double-blind treatment phase will be based on the treatments that the subjects actually received at the double-blind treatment phase. Summaries for the open-label extension phase will also be based on the treatment sequences that the subjects actually received during overall study phase, e.g. Acthar/Acthar and Placebo/Acthar.
- Study Day 1 is defined as the date of the first dose of IMP at the double-blind treatment phase. Study days are calculated as the difference between the date of interest and Study Day 1 plus 1 day. For events before Study Day 1, study days will be calculated as the difference in days between Study Day 1 and the date of interest. The day before the date of the first dose at the double-blind treatment phase will be defined as Day -1. This means there will be no study Day 0.

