4.4.3. Open-label Safety Population

The Open-label Safety Population includes subjects who continue into open-label extension phase and receive at least one dose of IMP during the open-label extension phase. The Open-label Safety Population will be used for all the safety and efficacy analyses for open-label extension phase and will be based on the actual treatment sequences received during the overall study phase (Acthar/Acthar or Placebo/Acthar) and total.

5. Subject Disposition

A summary of analysis populations will be presented by treatment group and total for all randomized subjects, the mITT population, the safety population, and open-label safety population. Summary of subject disposition will be presented for double-blind treatment phase and open-label extension phase separately.

Disposition of all randomized subjects in double-blind treatment phase will be summarized by treatment group and total descriptively, including summaries of the number and percentage of subjects who completed the double-blind treatment phase, subjects who continued into the open-label extension phase, subjects who early terminated from the double-blind treatment phase and the reasons for early termination from the double-blind treatment.

In addition, disposition of subjects participating in the optional open-label extension phase will be summarized by actual treatment sequences and total descriptively, including summaries of the number and percentage of subjects who completed the double-blind treatment phase, subjects who continued into the open-label extension phase, subjects who completed the open-label extension phase, and subjects who early terminated from the open-label extension phase. The reasons for early termination from the open-label extension will also be summarized.

The reasons for early termination from the double-blind treatment and the reasons for early termination from the open label extension will be summarized based on the following categories:

- Adverse event
- Death
- Lack of efficacy
- Lost to follow-up
- Met withdrawal criteria
- Non-compliance with study drug
- Physician decision
- Protocol violation
- Study terminated by sponsor

- Withdrawal by subject
- Other

Subject disposition for all randomized subjects and subject disposition for open-label safety population will be provided in by-subject listing, respectively.

6. Protocol Deviations

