All safety analyses will be conducted using safety population for the double-blind treatment phase and open-label safety population for the open-label extension phase separately. No imputation will be applied for missing data on any safety results. Missing or partially missing adverse event start dates will be imputed for treatment-emergent AE (TEAE) justification, refer to Appendix [15.1.1](#) for imputation details. All safety data will be presented in listings based on the safety population in the double-blind treatment phase and in the open-label extension phase, respectively.

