10.1. Adverse Events

An AE is any untoward or undesirable medical occurrence in a subject who is administered an IMP, which does not necessarily have to have a causal relationship with this treatment.

A TEAE is defined as an event that begins or worsens on or after the start of study drug through 30 days after the date of the last dose. The first dose of IMP at the open-label extension phase will be used as cutoff date, the TEAEs started before the cutoff date will be summarized in the double-blind treatment phase and the TEAEs started on or after the cutoff date will be summarized in the open-label extension phase; Subjects who did not continue into the open-label extension phase will be summarized in the double-blind treatment phase only.

If a subject experiences the same AE more than once with different severity, then the event with the highest severity level will be tabulated in “by severity” tables. If a subject experiences the same AE more than once with different relationship to study drug, then the event with the most related level will be tabulated in “by relationship” tables. Note that AEs with a missing severity will be considered as severe, and AEs with missing relationship will be considered as related to study drug. Adverse events are considered treatment-related if the relationship to study drug is possibly related, related or missing.

The incidence of AEs will be summarized in tables with the number and percentage of subjects with AEs by SOC and PT. At each level of SOC or PT, a subject with multiple events will only be counted once per SOC or PT. Percentages of subjects with AEs will be calculated out of the number of subjects in the safety population. SOC will be presented alphabetically and PTs within each SOC will be presented in decreasing order of frequency based on the total number of subjects with each AE in the Acthar group. The following categories of TEAE will be summarized by SOC and PT by treatment group and total for the double-blind treatment phase and the open-label extension phase separately:

- TEAEs
- TEAEs by severity (Mild, Moderate, and Severe)
- TEAEs by relationship (Not Related, Unlikely Related, Possibly Related, and Related)
- Treatment related TEAEs
- Serious TEAEs
- Serious TEAEs by relationship (Not Related, Unlikely Related, Possibly Related, and Related)
- TEAEs leading to study drug discontinuation
- TEAEs leading to death

Overview tables of the above categories will also be provided.

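### The AE partial-date rule is anchored only to the first double-blind dose, so some extension-phase events with incomplete start dates are counted in the double-blind tables

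*SAP*

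**What the plan says.** **Imputation (SAP 15.1.1).** Each branch compares the partial start date with a single first dose.
- Day missing, month of first dose: set to the day of that dose.
- Day missing, any later month: "then it will be imputed as the first day of the collected month".
- Day and month missing: the first-dose date if the year matches, or 1 January if the year is later.
- Whole date missing: the first-dose date.

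No branch mentions the open-label dose. The section does not define first dose, but SAP 4.3 points to the double-blind one: "Study Day 1 is defined as the date of the first dose of IMP at the double-blind treatment phase".

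**Phase assignment (SAP 10.1).** "The first dose of IMP at the open-label extension phase will be used as cutoff date". Events are then allocated by their start date. For those with an earlier start, "the TEAEs started before the cutoff date will be summarized in the double-blind treatment phase"; an event that starts on or after that dose goes to the extension tables.

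**Purpose (SAP Section 10, opening paragraph).** "Missing or partially missing adverse event start dates will be imputed for treatment-emergent AE (TEAE) justification". Phase is not mentioned.

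**Extension groups (SAP 4.4.3).** Extension summaries follow the "actual treatment sequences received during the overall study phase (Acthar/Acthar or Placebo/Acthar) and total".

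**The concern.** Two rules meet without being joined. One completes the start date with no regard to the extension, and the other uses that date to decide the phase. In the month when a subject crosses over, an event with a missing day is placed on the 1st, before the cutoff in nearly every case.

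For a placebo subject the crossover is the first exposure to Acthar. An event that began after that dose can thus appear in the placebo column of the double-blind tables, which hold the only randomised safety comparison. At the first double-blind dose the SAP settles the same doubt the other way, by imputing to the dose date.

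**Working it through.** The documents give no figure on this point, so the rules were applied as written.

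**1. Which branch applies.** The double-blind phase is 24 weeks (SAP 3.1), or 24 × 7 = 168 days, with a ±5-day visit window (protocol Table 1). The extension thus starts about 163 to 173 days after the first dose. No month exceeds 31 days, so the crossover month is never the first-dose month. A missing day in it always becomes the 1st.

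**2. Which phase follows.** The 1st is before the cutoff unless the cutoff is itself the 1st, when the on-or-after wording puts the event in the extension. The end-date override in 15.1.1 can only move a start earlier, so it cannot correct the phase.

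**3. Example (assumed dates).** First dose 6 January 2020; extension start 168 days later, 22 June 2020.

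| Start as recorded | Imputed start | Phase |
|---|---|---|
| June 2020 | 1 June 2020 | Double-blind |
| 2020 only | 6 January 2020 | Double-blind |
| Nothing | 6 January 2020 | Double-blind |
| July 2020 | 1 July 2020 | Extension |

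**4. All start dates.** Assumptions: every first-dose date from 1 January 2018 to 31 December 2021 (1,461 dates), extension start 163, 168, 169 or 173 days later, and onset uniform over days. All four offsets gave the same results.
- Extension starting on the 1st: 48/1,461 = 3.3%.
- True extension onsets in the crossover month, day missing: 21,520/22,981 = 93.6% sent to the double-blind phase.
- True extension onsets over 24 weeks plus 30 days (168 + 30 = 198 days), day missing: 21,520/(1,461 × 198) = 21,520/289,278 = 7.4%.
- Same window, day and month missing: about 73%.
- Whole date missing: 100%.
- True double-blind onsets in the crossover month, day missing: 0% sent to the extension.

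**5. Effect of a bare correction.** Imputing every missing-day event of the crossover month to the cutoff lowers the 93.6% to 0%. It also moves 100% of that month's true double-blind onsets into the extension. Any repair therefore needs checks on whether the event began earlier.

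**6. Weight of one event.** SAP 4.1 gives 55 randomised subjects. With an even split (assumed), one extra subject with a given event changes that arm's rate by 1/27.5 = 3.6 percentage points.

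**The case against.** **The imputation serves treatment-emergent status only.** For that purpose the first of the month is adequate, since any later month is after the first dose. This stands as far as it goes. But SAP 10.1 needs a start date to allocate phase, and the SAP offers no other date for these events.

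**First dose could be read as phase-specific.** That would be circular, because the phase depends on the start date. SAP 4.3 and 10.1 also name the extension explicitly when they mean its first dose.

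**Few events will be affected.** This stands. Protocol 16.4 asks for date and time of onset, events are elicited at every visit, missing data are queried (protocol 21.2), and the first open-label dose is given in clinic with at least an hour of observation. Immediate reactions should be fully dated. The AE tables are descriptive, and all events are listed by phase.

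**The rule is neutral between arms.** This also stands. A reader might infer that the rule always raises placebo rates relative to Acthar. The documents do not support that: Acthar/Acthar subjects have extension events moved into the double-blind Acthar column by the same mechanism, so the net effect on the contrast depends on the mix.

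**A repair can err the other way.** It can, for ongoing events that began just before the cutoff. Hence the conditions in the fix.

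**Conclusion.** The gap is real and minor. Following SAP 15.1.1 and 10.1 literally moves some extension events with incomplete start dates into the double-blind tables, and for missing-day events never the reverse.

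The 93.6% is not a share of adverse events: it applies only to events with a missing day and true onset between the cutoff and the end of the crossover month. Across the whole extension window the corresponding figure is 7.4% of missing-day events. Both rest on uniform onset and assumed calendar dates. The 7.4% would be higher if onsets cluster soon after first exposure. The documents do not say how many events have partial dates, so no change in an arm's rate can be estimated. The cutoff is itself an estimate under SAP 4.3, which adds error but does not remove the problem.

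**What to change.** Add a phase-assignment rule to SAP 15.1.1, using the estimated first open-label dose date of SAP 4.3 as the cutoff. It applies when all three conditions hold:
- the known part of the start date is compatible with onset on or after the cutoff;
- the stop date is not before the cutoff;
- the event was not already reported at or before Visit 8.

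The start is then imputed, for phase assignment, as the cutoff date if the cutoff falls within the recorded partial date, and otherwise as the earliest compatible date after it. All other partial-date events stay in the double-blind phase. Where the visit of first report is not available, use the stop-date check alone and flag these events in the listing. Protocol 16.4 does not name that visit among the AE page fields, so availability must be confirmed.

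State the downside: with the stop-date check alone, some ongoing events that began just before the cutoff will be counted in the extension. The SAP already accepts the same lean toward exposure at the first double-blind dose.

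The cost is a few lines in the appendix, a small programming change and a listing flag. SAP 15.1.2 uses the same single anchor for medication start dates and should be checked at the same time.

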15.1.2. Prior/Concomitant Medications

Missing start dates for concomitant medications data will be handled as follows:

- Missing day only:

- If the month and year are the same as the first dose month and year, then it will be imputed as the date of first dose.
- If either the year is the same as the first dose year but the month is prior to the first dose month or the year is prior to the first dose year, then it will be imputed as the last day of the collected month.
- If either the year is the same as the first dose year but the month is after the first dose month or the year is after the first dose year, then it will be imputed as the first day of the collected month.
- Missing month:
 - If the year is the same as the first dose year, then it will be imputed as the date of first dose.
 - If the year is prior to the first dose year, then it will be imputed as December.
 - If the year is after the first dose year, then it will be imputed as January.
- Missing day and month:
 - If the year is the same as the first dose year, then it will be imputed as the date of first dose.
 - If the year is prior to the first dose year, then it will be imputed as December 31st of the collected year.
 - If the year is after the first dose year, then it will be imputed as January 1st of the collected year.
- Missing day, month and year:
 - It will be imputed as the date of first dose.

Missing stop dates for concomitant medications data will be handled as follows:

- Missing day only:
 - It will be imputed as the last day of the collected month or the death date, whichever is earlier.
- Missing day and month:

- It will be imputed as December 31st of the collected year or the death date, whichever is earlier.
- Missing day, month and year:
 - No imputation is needed.

If the imputed start date is after the stop date, then the start date will be imputed as the stop date.

